8.1.10 Week 52 Safety Follow-up (± 7 days)

All participants returning for week 52 (who are not going into the Open-Label Extension phase) will undergo the following procedures after the Week 48 visit is completed in person:

- Physical exam
- Vital signs (sitting blood pressure, pulse, temperature, respiration rate)
- Weight
- Documentation of concomitant treatment
- Documentation of adverse events
- Blood samples for safety laboratory tests (hematology and serum chemistry, as listed in Section 8.2)
- Resting 12-lead ECG
- Sheehan Suicidality Tracking Scale

8.1.11 Unscheduled Visit

Documentation of concomitant medication, adverse events, and vital signs will be collected at all unscheduled visits, and additional clinical safety laboratories may be completed at the discretion of the PI or at the request of the medical monitor. Participants returning to conduct an unscheduled visit outside of the protocol's visit schedule may have missing or additional study procedures performed by site personnel.

8.1.12 Open-Label Extension Phase (as applicable)

The Extension Phase is an optional open-label 48-week treatment phase. The investigator will be responsible for evaluating any major changes in the participant's status to determine their participation in the open-label extension. This should be based on the status of the participant at the end of the double-blind phase, the participant's risk-benefit profile as determined by the site PI, the consent of the participant, and the integrity of the trial.

If the participant has completed the double blind treatment phase prior to the Open-Label Extension Phase being approved at their study center, they can re-consent and start the study as long as the investigator determines that open-label treatment offers an acceptable risk-benefit profile for the individual. Once the study site is open for recruitment for the Open-Label extension, participants that completed the study prior will have up to 12 weeks to enroll in the Open-Label study.

When sites have opened for recruitment for the Open-Label Extension Phase, participants completing the double-blind treatment phase must go directly from the Week 48 visit into the Extension Phase if they choose and are eligible to continue.

 Participants who are completing the double-blind treatment phase may directly enter the Open-Label Extension phase. These participants should not complete the follow-up safety visit at Week 52 (of the double-blind treatment phase). Instead, these participants should continue directly into the Open-Label Extension phase starting at Week 48 (of the double-blind treatment phase). The Week 48 visit will also serve as the Baseline visit in the Extension Phase for participants who are going directly from the double-blind treatment phase to the OLE. Thereafter, participants will undergo visits at Week 4, Week 8, Week 12, and then every 12 weeks of the Extension Phase as outlined in Table 3 (Schedule of Assessments/Time & Events- Extension Phase).

- Participants who previously completed the double-blind treatment phase prior to the Open-Label Extension phase of the study being open for recruitment at their study center, may also enter the Open-Label Extension (OLE) phase.
 - o For participants who will have been off of the study drug for less than or equal to 4 weeks, the subject should come into the investigative site for an Abbreviated Drug Dispensation Visit (also "Abbreviated OLE Baseline Visit"), at which time any major medical or medications changes will be reviewed prior to dispensing riluzole. In this case, most procedures from the Week 48 visit will also serve as the OLE Phase Baseline visit, as outlined in Table 3 (Schedule of Assessments/Time & Events-Extension Phase). Thereafter, participants will undergo visits at Week 4, Week 8, Week 12, and then every 12 weeks of the OLE Phase
 - o For participants who have been off the study drug for greater than 4 weeks, these participants should be re-assessed and re-consented by the PI during an OLE Baseline Visit. From the date that the Open-Label Extension is open for recruitment at the study site, these participants that completed the study prior will have up to approximately 12 weeks to complete the OLE Baseline Visit. Thereafter, participants will undergo visits at Week 4, Week 8, Week 12, and then every 12 weeks of the OLE phase as outlined in Table 3 (Schedule of Assessments/Time & Events-Extension Phase). All previous completers of the double-blind phase will have a 12-week window of opportunity to baseline into the OLE, regardless of their date of double-blind phase completion. In the event sites open for OLE recruitment, then close due to COVID-19 before enrolling all prior completers, exceptions to the 12-week window will be considered on a case-by-case basis, following discussion with the Sponsor Medical Monitor:

Sponsor Medical Monitor PPD PPD Cell: PPD PPD

 As with the double-blind phase, certain provisions may be implemented, in order to minimize potential hazards to study participants due to COVID-19. These provisions may allow alternatives to in-person study visits and include but are not limited to the following: conducting remote visits via phone/telemedicine video, focusing on safety assessments during remote visits, performing safety labs via local labs or professional in home phlebotomy vendors, and shipping study medication to study subjects if needed. Any potential issues should be discussed with the Sponsor and will be addressed on an individualized basis.

- OLE visits may be completed remotely, if necessary due to COVID-19. However, participants should not be on study drug for greater than 24 weeks without completing an in-person visit. For these participants, IP should be held or the participant discontinued.
- Participants who early-terminated from the double-blind phase trial or discontinued the study drug for any reason will not eligible for enrollment into the OLE phase.
- All participants must have their Week 48 visit in person prior to enrolling in the OLE phase.
 (Due to COVID-19, the timing of this visit may be delayed)

All participants entering the OLE phase will start with one capsule of BHV-4157 per day and titrate to two capsules per day after week two. This will be done so that all participants will be on open-label medication and will safely continue from either active BHV-4157 or placebo.

All participants in the Open-Label Extension phase are planned to undergo a termination visit two weeks after the last dose of study drug.

8.2 Laboratory Safety Assessments

Clinical Safety Laboratory tests will be performed by a Central Laboratory. Assessments include the following:

Hematology:

Hemoglobin, hematocrit, platelet count, RBC, WBC, differential count and absolute neutrophil count

Chemistry:

Sodium, potassium, chloride, calcium, ALT, AST, LDH, alkaline phosphatase, GGT, phosphorous, bicarbonate, CPK, total protein, albumin, direct bilirubin, indirect bilirubin, total bilirubin, glucose, creatinine, BUN, uric acid, total cholesterol, LDL, HDL, triglycerides (lipids collected only during double-blind phase), B12 (at screening only), folate (at screening only)

Urinalysis:

pH, specific gravity, protein, glucose, ketones, urobilinogen, bilirubin, blood

An approximate blood volume of 9.5 ml at screening and 7 mL at subsequent study visits (baseline, week 4, week 8, week 12, week 24, and week 48, Open-Label Extension phase week 4, week 8, week 12, week 36, and week 48), will be collected for serum chemistry and hematology analyses. If vitamin B12 is below normal and the Investigator thinks it necessary, an additional blood (approximately 5 ml) may be taken to measure serum methylmalonic acid levels at another visit during screening period.

Urine will be collected for urinalysis at screening, baseline, week 4, week 12, week 24 and week 48, and Open-Label Extension phase week 4, week 8, week 12, week 24, and week 48.

The Central Laboratory will provide the investigational sites with all appropriate materials for specimen collection, sample processing, packaging and shipping. Full details of sampling (blood and urine), sample preparation and storage methods will be given in the laboratory manual.

If a participant is unable to come in to the study site and needs to have safety labs conducted locally, this is acceptable. The study site should provide the participant or local laboratory with a requisition and should collect the results. A home phlebotomist may also be an option for participants if needed.

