1.7.1.3 Elevations in Liver Function Tests

BHV-4157 has not been associated with significant changes in liver function or pathology in nonclinical toxicology studies to date, as reflected in the Investigator's Brochure. No clinically significant LFT changes were observed on study drug in BHV4157-101. No participant had AST or ALT laboratory abnormalities > 3 X ULN in BHV4157-102, BHV4157-103 or BHV4157-201. BHV4157-203, BHV4157-206, and BHV4157-207 are blinded and ongoing. Preliminary safety findings are based on available randomized, double-blind data. As of 22-Jan-2020, 1 subject discontinued from BHV4157-207 and 1 subject discontinued from BHV4157-203 due to increased liver function tests.

Riluzole is associated with elevations in aminotransferases that have been reflected in monitoring precautions that will be followed within this protocol. Experience in almost 800 ALS patients indicates that about 50% of riluzole-treated patients will experience at least one ALT/SGPT level above the upper limit of normal, about 8% will have elevations > 3 X ULN, and about 2% of patients will have elevations > 5 X ULN. A single non-ALS patient with epilepsy treated with concomitant carbamazepine and phenobarbital experienced marked, rapid elevations of liver enzymes with jaundice (ALT 26 X ULN, AST 17 X ULN, and bilirubin 11 X ULN) four months after starting riluzole; these returned to normal 7 weeks after treatment discontinuation. Maximum increases in serum ALT usually occurred within 3 months after the start of riluzole therapy and were usually transient when < 5 X ULN. In trials, if ALT levels were < 5 X ULN, treatment continued and ALT levels usually returned to below 2 X ULN within 2 to 6 months. Treatment in studies was discontinued, however, if ALT levels exceeded 5 X ULN, so that there is no experience with continued treatment of ALS patients once ALT values exceed 5 X ULN. There were rare instances of jaundice. There is limited experience with rechallenge of patients who have had riluzole discontinued for ALT > 5 X ULN, but there is the possibility of increased ALT values reoccurring. Therefore, rechallenge is not recommended. In post-marketing experience, cases of clinical hepatitis associated with riluzole have been reported, including one with fatal outcome.

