 - Week 24 and week 48 vMRI: the protocol window for vMRI at week 24 and week 48 is 14 days before and up to 14 days after the clinic visit. If participant is terminating early at 36 week or after, obtain vMRI if MRI is performed on the same day as a lumbar puncture at week 48, the vMRI must be conducted before the lumbar puncture. Otherwise, at least a 3-day window between vMRI and the lumbar puncture is required.
- 12 It is anticipated that lumbar puncture will be performed on an estimated 100 study participants as part of a sub-study (separate informed consent required).
- Only for the CSF sub-study. Visit windows for CSF are: up to 14 days prior to first dose of study medication and up to 14 days prior to weeks 24 and 48. If a participant in the CSF sub-study is terminating early, they do not need to undergo lumbar puncture.
- Post lumbar puncture safety follow up telephone call must occur 1 to 3 days after the lumbar puncture is performed.
- First dose of study medication will be given in the clinic at the baseline clinic visit after completion of the baseline visit procedures.
- Participants will receive a phone call during Week 2 from site study personnel in order to assess study drug tolerability. If tolerable, then the participant will be instructed to proceed with dose escalation.
- 17 Treatment blinding questionnaire to be administered to site PI and Raters.

Table 3: Schedule of Assessments and Events – Open-Label Extension Phase

Visit Number	1	2	3	4	5	6	7	8	9	10	
Study Visit Timepoint	Baselinel	Abbrev- iated Drug Dispensat ion Visit ²	Ext Week 2 (+/- 7 days)	Ext Week 4 (+/- 7 days)	Ext Week 8 ³ (+/- 7 days)	Ext Week 12 (+/- 7 days)	Ext Week 24 (+/- 7 days)	Ext Week 36 (+/- 7 days)	Ext Week 48 or Early Term (+/- 7 days)	Week2 Post last dose (+/- 7 days)	Unsched- uled Visit ⁴ (+/- 7 days)
Informed Consent	X	X									
Medical History	X										
Adverse Event Assessment	X	X	X	X	X^3	X	X	X	X	X	X
Telephone Check-in ⁵ Includes AE assessment and concomitant medication review			X		X ³						
Laboratory Assessments ⁶	X			X	X^3	X	X	X	X		
Urinalysis	X						X		X		
Physical Exam	X								X		
Physical Measurement - Weight	X						X		X		
Vital Signs	X	X		X		X	X	X	X	X	X
12-Lead ECG	X					X	X		X		
Concomitant Medication Review	X	X	X	X	X	X	X	X	X	X	X
Sheehan Suicidality Tracking Scale (S-STS)	X	X		X		X	X	X	X	X	
Dispense Study Drug	X	X		X		X	X	X			
Volumetric MRI ⁷	X								X		
ADAS-Cog 11	X						X		X		
CDR-SOB	X						X		X		

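### Protocol 8.2 and the extension schedule in Table 3 contradict each other on the visits for safety blood tests and urinalysis

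*Protocol*

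**What the plan says.** Protocol 8.2 names the visits at which blood "will be collected for serum chemistry and hematology analyses". For the extension these are "Open-Label Extension phase week 4, week 8, week 12, week 36, and week 48". The chemistry panel in the same section contains the liver tests: "Sodium, potassium, chloride, calcium, ALT, AST, LDH, alkaline phosphatase, GGT", with the bilirubin fractions later in the list.

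Table 3 in Protocol Appendix I has a row "Laboratory Assessments", marked at baseline and extension Weeks 4, 8, 12, 24, 36 and 48. Both SAP copies of that table (SAP Appendix 1) mark the same visits. SAP Table 5 (section 4.3.8) sets extension windows for laboratory assessments at Weeks 4, 8, 12, 24, 36 and 48. Protocol 12.7.4 names the same six weeks for its laboratory shift tables, although that section is not clearly confined to the extension.

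For extension urine, 8.2 gives "Open-Label Extension phase week 4, week 8, week 12, week 24, and week 48". The urinalysis row of Table 3 is marked at baseline, Week 24 and Week 48 only.

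On which source sites should use, section 8.1.12 says "participants will undergo visits at Week 4, Week 8, Week 12, and then every 12 weeks" and refers to Table 3 by name. Section 2 does the same.

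**The concern.** Section 8.2 is the protocol's own laboratory safety section, and its list differs from the schedule for the same phase. Nothing in the text explains why Week 24 is missing from the blood list while it is present in the urine list of the following paragraph. No statement says which source prevails if they differ.

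The subject is one the protocol treats as a known risk. Section 1.7.1.3 says that aminotransferase elevations under riluzole are reflected in "monitoring precautions that will be followed within this protocol". The extension also contains people with no previous exposure: former placebo participants start the drug there. If sites worked from different lists, participants in the same phase would be monitored on different schedules, and the by-visit laboratory summary at extension Week 24 would lack scheduled values from some of them.

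**Working it through.** The plan states no figure to reproduce. The check compares the visit lists and takes the intervals between consecutive scheduled collections.

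**1. Lists side by side (extension weeks; 0 = extension baseline)**

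| | Protocol 8.2 | Table 3 |
|---|---|---|
| Chemistry and hematology | 4, 8, 12, 36, 48 | 0, 4, 8, 12, 24, 36, 48 |
| Urinalysis | 4, 8, 12, 24, 48 | 0, 24, 48 |

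8.2 names no separate extension baseline. For participants who go straight into the extension, the double-blind Week 48 visit serves as baseline, and 8.2 does list that visit. The comparison that matters is therefore after baseline:

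- Blood: Table 3 has Week 24 and 8.2 does not. 8.2 has no visit that Table 3 lacks.
- Urine: 8.2 has Weeks 4, 8 and 12 and Table 3 does not. Both have Weeks 24 and 48.

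**2. Intervals between scheduled blood draws, counted from extension baseline**

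- 8.2: 4, 4, 4, 36 − 12 = 24, 48 − 36 = 12 weeks. Longest: 24 weeks.
- Table 3: 4, 4, 4, 12, 12, 12 weeks. Longest: 12 weeks.

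With the visit window of 7 days either side at each end:

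- 24 weeks = 168 days; 168 ± 14 = 154 to 182 days, or 22 to 26 weeks.
- 12 weeks = 84 days; 84 ± 14 = 70 to 98 days, or 10 to 14 weeks.

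**3. Effect on the SAP Week 24 extension window (Day 127-210)**

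- Week 12: Day 84 ± 7 = Day 77 to 91, inside the Week 12 window (Day 71-126).
- Week 36: Day 252 ± 7 = Day 245 to 259, inside the Week 36 window (Day 211-294).

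Neither draw can fall in Day 127-210 while it stays within its visit window. A participant followed only by the 8.2 list contributes no scheduled blood result to that window.

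**4. The same interval elsewhere**

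The double-blind blood list in 8.2 is baseline and Weeks 4, 8, 12, 24 and 48, so its longest interval is 48 − 24 = 24 weeks. A footnote to Table 1 urges, but does not require, a double-blind Week 36 draw.

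**5. Who could be affected**

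About 168 participants are randomised to placebo. At the 26% dropout assumed in Protocol 12.1.1, 168 × 0.74 = 124 would complete. 124 / 336 = 37% of all randomised, and that would require every placebo completer to be eligible and to choose to continue.

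**The case against.** The best case against giving this weight is that 8.2 was never meant to set timing. Its list sits in parentheses in a sentence about blood volume, and the visit sections cite 8.2 for the content of the panel. Section 8.1.10 requires Week 52 safety bloods and cites 8.2, yet Week 52 is not in the 8.2 list, so 8.2 is already incomplete as a calendar. For the extension, sections 2 and 8.1.12 name Table 3, and section 8.1 points to Appendix I. The other sources agree on Week 24 bloods. Section 8.1.11 also allows discretionary laboratory tests at unscheduled visits, and 8.2 leaves sampling details to a laboratory manual that is not available here. Most of this stands, and it is why the practical effect is probably small. It does not remove the contradiction: 8.2 still says at which visits blood and urine are collected.

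A reader might infer three stronger things that the documents do not support.

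- **That the extension actually has a 24-week gap in liver testing.** It does so only for a site that works from 8.2 and passes over the references to Table 3.
- **That half of the randomised participants are first exposed under the thinner schedule.** The extension is optional, needs new consent and the investigator's risk-benefit judgement, and is closed to those who terminated early or discontinued study drug. Step 5 gives the resulting ceiling at the assumed dropout.
- **That the gap falls where liver risk peaks, or that 24 weeks is in itself an error.** Section 1.7.1.3 says the largest ALT rises on riluzole usually came within 3 months of starting, and both lists have Weeks 4, 8 and 12. The double-blind list in 8.2 contains the same interval.

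**Conclusion.** The contradiction is certain; its practical weight is minor. Protocol 8.2 and Table 3 give different extension visits for chemistry and hematology (Week 24) and for urinalysis (Weeks 4, 8 and 12, and baseline). For a site that used 8.2, the longest interval between scheduled liver tests would double from 12 to 24 weeks, and the SAP Week 24 window would receive no scheduled blood result.

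This rests on two conditions: that some site takes its timing from 8.2, and that no unscheduled draw fills the gap. The documents do not show how likely either is. Co-primary endpoints, power and type I error are untouched. The check does not establish which testing frequency is right.

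**What to change.** Reconcile the extension blood-test and urinalysis lists in 8.2 with Table 3 so that both give one schedule, and state whether 8.2 or Appendix I governs timing. Which schedule applies is the sponsor's clinical decision.

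Then check the result against the SAP. For blood, the Table 5 windows, the SAP copies of the schedule and the weeks in Protocol 12.7.4 all include Week 24, so they agree with Table 3 and would need to change only if that visit were not retained. For urinalysis, which SAP 4.10.3 treats as laboratory data, the Table 5 windows at Weeks 4, 8 and 12 hold scheduled samples under 8.2 but not under Table 3, and the Week 36 window holds none under either. The SAP should say which windows apply to urine.

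The Week 52 omission from the 8.2 blood list can be reconciled with Table 1 and section 8.1.10 in the same pass. The cost is a wording correction or a clarification letter to sites, with a one-line SAP note if the windows are affected.

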8.3 Pharmacokinetic Assessments

A plasma sample for pharmacokinetic (PK) should be collected at baseline, week 4, week 8, week 12, week 24, and week 48 of the double-blind phase of the trial. Participants should take their dose at their routine time on the days of these visits. Date and time of last dose should be collected in case report forms for entry into the EDC system. Participants who are able to be scheduled for a morning visit should be instructed to hold their dose of study drug that morning until after a PK trough sample is obtained, if possible and appropriate in the judgment of the investigator.

PK samples should be drawn if there are any SAEs that could possibly be drug-related or severe AEs that could be drug-related.

In addition, for participants undergoing lumbar puncture, plasma samples for PK should be drawn at the time of lumbar puncture for Week 24 and Week 48 visits for the double blind placebo phase. Date and time of last dose should be collected in case report forms for entry into the EDC system.

There is no PK sampling during the OLE phase.

8.4 Physical and Neurological Examination

A physical examination will be performed by a medically qualified professional at every study visit. A review of the major body systems will be performed and vital signs will be assessed. A neurological examination will only be performed at screening and will include assessment of motor strength, sensory, deep tendon, tremor, cerebellar, cranial, and mental status.

8.5 Genotyping

ApoE (e4 +/-) genotype is associated with the risk and age of onset of AD. ApoE genotyping will be performed at screening. The blood collection will total approximately 10 mL. Results of ApoE genotyping will be used in exploratory subgroup analyses to explore the relationship between ApoE genotype clinical course and response to treatment.

If a participant has agreed to allow his/her sample to be banked, then the DNA sample will be stored at the UCSD and used for additional genetic testing. Samples will be de-identified prior to being shared with outside investigators to preserve the confidentiality of participants. Participants can request in writing any time to have their samples destroyed. Results of this testing are for research purposes only and will not be disclosed to the participant or study partner.

8.6 Electrocardiogram

A standard 12-lead resting ECG will be performed during screening, week 12, week 24, and week 48 of the Open-Label Extension phase. The Investigator or designee will review the 12-lead ECG and findings will be recorded in the eCRF as normal, abnormal but not clinically significant, or abnormal and clinically significant. Any clinically significant abnormalities on ECGs recorded after administration of the investigational product will also be documented as AEs and entered on the AE page of the eCRF. Clinically significant abnormalities on ECGs prior to administration of the investigational product, will be recorded as medical history.

8.7 vMRI Assessments

Brain structural change is seen in normal aging, but is accelerated in neurodegenerative disease, including AD. Atrophy in AD arises from neuron and synapse loss that begins in the entorhinal cortex. The pathology then spreads throughout the limbic regions of the temporal lobe, including the hippocampal formation. Subsequently, neuron loss and atrophy is observed throughout neocortical association areas in temporal, parietal and frontal lobes.

vMRI allows the *in vivo* assessment of brain structure volume and provides a measure of atrophy rate. Results from vMRI studies suggest that the patterns of atrophy in AD, which mirror the pathological progression of the disease, can reliably be detected and tracked across time. Atrophy of the medial temporal lobe, including hippocampus and entorhinal cortex, has long been described in vMRI studies of AD. Hippocampal volume derived from MRI correlates with histological hippocampal volume and degree of neuronal loss and AD pathology, and entorhinal cortical thickness change appears to be an early and sensitive indicator of neurodegeneration associated with AD (Holland et al., 2009; Jack et al., 2004). Longitudinal MRI measures of regional and whole-brain volumetric change provide a valuable complement to cognitive measures in that they are not influenced by temporary symptomatic improvements, and they provide an early index of the study drug's ability to reach the target organ and have an effect on AD-related atrophy.

Participants will undergo vMRI scans of the brain at screening, week 24 and week 48 (and Extension Phase baseline and week 48) in order to assess for changes in brain volumes that may be associated with clinical change due to treatment with BHV-4157.

Volumetric MRI scans will use the same imaging protocol, which will include a localizer scan, a 3D T1- weighted sagittal acquisition (MPRAGE or IR-SPGR), a T2-weighted FLAIR axial acquisition, a T2* gradient recalled echo axial acquisition for magnetic susceptibility, and a diffusion weighted axial acquisition to assess for restricted diffusion.

Images will be checked for image quality and adherence to scanning protocols. 3D T1-weighted datasets passing quality checks will be corrected for spatial distortion and for intensity variation. Screening and follow-up datasets for each participant will be spatially registered to one another using rigid-body registration followed by nonlinear registration and neuroanatomic parcellation to quantify whole-brain and subregional volumetric change on a patient-by-patient basis.

The local MRI results will determine eligibility for each participant in the double blind treatment phase of the trial when the PI will confirm if MRI results are consistent with AD, meet the specified inclusion criteria, and do not have exclusionary findings as defined by the protocol. It is the responsibility of the PI to make this determination following review of the MRI, and to sign as well as date the local radiology report or the PI's own brain MRI written evaluation to acknowledge their review. The PI is at liberty to consult with a local neuroradiologist, however there is no requirement for a formal MRI read from a neuroradiologist. The ADCS Medical Safety team, or ADCS Imaging core are available to address any questions surrounding MRI eligibility. If there are safety concerns identified on this MRI, the PI should communicate with the participant's Primary Care Physician and consult with ADCS Medical Monitor, ADCS Director, and ADCS Imaging Core.

Whole brain volume (WBV, excluding cerebellum), bilateral ventricular volume and bilateral hippocampal volume will be measured. Quantitative anatomical regional change (Quarc) will be used as the computational MR image processing application. Detail for the statistical computations is given in the Statistical Analytical Plan (SAP).

If performed on the same day as a lumbar puncture, the vMRI should be conducted before the lumbar puncture. Otherwise, at least a 3-day window between vMRI and the lumbar puncture is required. Scanners that have passed the study's qualification procedures will be used. Participants must be scanned by the same scanner throughout the study.

Participants with a contraindication to MRI at the time of screening are deemed ineligible to participate in this study. Participants may continue to participate on the study if they have already been randomized but develop a contraindication to MRI during the course of the study.

